## 5.0 Analysis Population

A total of 315 adolescents 12.0 to 18.0 years of age ( $n = \sim 105$  / group for 3 IV groups) will be needed for this study. The samples used for analysis are as follows:

- Sample 1. All JFM subjects with a diagnosis of fibromyalgia consistent with current American College of Rheumatology criteria, irrespective of intervention group (n = 315).
- Sample 2. All JFM subjects receiving the FIT Teens intervention (n = 105).
- Sample 3. All JFM subjects receiving the CBT treatment (n = 105).
- Sample 4. All JFM subjects receiving the GAE treatment (n = 105).

#### 6.0 Statistical Analyses

Analyses will be carried out on the full intent-to-treat sample (Sample 1) as the primary analysis. Data analysis will begin with a review of all relevant variables in the dataset. For continuous variables, parametric as well as nonparametric measures of central tendency, variability, and association, will be computed. Distributional properties of potential outcomes will be evaluated and tested for normality where appropriate. Those differing markedly from normality will be considered candidates for transformation or alternative modeling techniques. Our analyses will be divided into three distinct sections. First (Primary Aims), the effectiveness of the FIT Teens intervention (Sample 2) for the reduction of functional disability will be compared with the other two treatments in several ways. FIT Teens will be compared to a CBT-only group (Sample 3) and GAE group (Sample 4) at 3-month follow-up (H1a, H1b). Additionally, differences between groups will be compared over time (i.e., 6, 9, 12-month follow-up; H2a, H2b), and analyses will be conducted to determine whether more patients in the FIT Teens intervention group obtain clinically meaningful improvement at 3-months when compared to the other two treatments (H3a, H3b).

Second, (Secondary Aims), the effectiveness of the FIT Teens intervention (Sample 2) for the reduction of pain intensity will be compared with the other two treatments (Samples 3 and 4) in several ways, similar to FDI analyses, including comparisons at 3-month follow-up (H4a, H4b), as well as whether these treatments are sustained over time (i.e., 6, 9, 12-month follow-up; H4c, H4d). Last, exploratory analyses also will be conducted to examine a mechanistic model of physical activity. Unless otherwise noted,  $\alpha = 0.05$  (two-sided) will serve as the criterion for statistical significance for all analyses. All data will be analyzed using the current version of MPlus.

## 6.1 Descriptive Statistics

Data analysis will begin with a review of all relevant variables in the dataset. For continuous variables, parametric measures of central tendency, variability, and association, will be computed. Distributional properties of potential outcomes will be evaluated and robust estimation techniques (MLR estimation, bootstrap resampling) will be used to guard against Type-1 errors that typically result from non-normal response variable data.

**Descriptive statistics.** Descriptive statistics (mean, median, std, min, max) will be computed for the following variables at each determined assessment time point: (with baseline only baseline only for demographics): e.g., AGE, INCOME, MEDTOT, CGA, PRFAVGPN\_RAW, FDITOT, CDITOT, PCSTOT, PCQTOT, TSKTOT, FATIG,

PAINBEH, PAININT, WPITOT, CARDSX, SSITOT, SOMSX, SSCHK, CASPETOT, BEIGHTON

**Frequency Counts/Percentages.** Frequency counts and percentages will be computed for the following variables: GROUP, FORMAT, SEX, RACE, ETHNIC, INCOME, INSURANCE, CRGVR1, EDU1, CRGVR2, EDU2, ENGRGRD, FMGROUP

## 6.2 Baseline Comparisons

Baseline group comparisons will be used to test for equivalence among the three intervention groups at baseline (Samples 1, 2, 3 by GROUP)

- One-way ANOVA/Kruskall Wallis: AGE, INCOME, RSOVERALL, FDITOT, APVAS, FDITOT, CDITOT, PCSTOT, PCQTOT, TSKTOT, FATIG, PAINBEH, INTERF, WPITOT, CARDSX, SSITOT, SOMSX, SSCHK, CASPETOT, BEIGHTON
- Chi-square/Exact Test: FORMAT, SEX, RACE, ETHNIC, INCOME, INSURANCE, CRGVR1, EDU1, CRGVR2, EDU2, ENGRGRD, FMGROUP

Specific tests used will depend on distributional properties and expected cell counts. Test results with p-values <.10 will be considered as candidates for inclusion in the multiple covariate models in the analyses below.

# 6.3 Primary Analyses

This research design constitutes a four-level model: repeated longitudinal assessments (level 1) are nested within participants (level 2) who are tested in cohorts of 4-6 participants (level 3) within each of the six study sites (level 4). Prior to testing the effects of treatment group on primary and secondary outcomes, Cohort (Level 3) and Site (Level 4) variation must be addressed appropriately. Study site serves only as a means to an end regarding recruitment of the requisite sample size. Cohort (level 3) is a unique design and implementation feature of group-based sessions that likely serves several beneficial purposes: social support from similar age peers, greater engagement and participation, decreased likelihood of dropout, amongst others. However, the primary aims concern only the efficacy of FIT-TEENS versus GAE and CBT at the level of the individual participant (level 2). As such, study site (level 4) and cohort (level 3) constitute statistical "nuisances" that must be dealt with correctly with to avoid biased treatment effects and subsequent inferential errors. Specifically, primary and secondary aims analyses will use generalized estimating equations for two reasons: 1.) continuous repose variables need not be normally distributed, and 2.) the random effects structure (i.e., covariance matrix) is not of interest. Specifically, every unique combination of participant (level 2), cohort (level 3), and site (level 4) will be used to indicate non-independent (i.e., correlated) responses in the GEE analyses.

Also, as noted in Study Design (Section 3.0), with the onset of COVID 19 restrictions in March 2020, all treatment arms will be delivered in remote format. A binary indicator variable (0= In-Person delivery; 1 = Remote Delivery) will be included as a moderator in all analyses to model the effect of delivery format. Further, the need for an indicator variable by independent variable group interaction term (e.g., format X GAE, format X CBT) to adjust for any potential deviations from the randomization plan due to the change in delivery format will be tested.

- **H1a** The FIT Teens group will show significantly greater reduction in functional disability at 3-month follow-up compared to CBT.
- **H1b** The FIT Teens group will show significantly greater reduction in functional disability at 3-month follow-up compared to GAE.

Results will be analyzed via a longitudinal GEE approach. Groups will be dummycoded with FIT as the reference class. It is hypothesized that significant and positive 'slope on group' coefficients for CBT and GAE indicating a significantly lower FDI for FIT vs. CBT & GAE. Non-independence of FDI scores will be addressed by specifying every unique combination of participant (level 2), cohort (level 3), and site (level 4) as indicators of non-independent (correlated) responses in the GEE syntax (i.e., in the 'Repeated =' syntax specification.

- **H2a** Functional disability in the FIT Teens group will remain significantly lower than CBT at 6-, 9- and 12-month follow-up.
- **H2b** Functional disability in the FIT Teens group will remain significantly lower than GAE at 6-, 9- and 12-month follow-up.

To test whether group differences on FDI scores are maintained over time, a longitudinal SEM approach will again be used. Groups will be dummy-coded with FIT as the reference class. Significant and positive 'intercept on CBT' & 'intercept on GAE' coefficients will indicate significantly lower FDI scores for FIT vs. CBT & FIT vs GAE at 6-, 9-, & 12-month assessments. Significant and positive 'slope on CBT' & 'slope on GAE' coefficients would indicate worsening FDI scores for CBT & GAE over time relative to FIT scores that have stayed the same or further improved. Nesting of clustered participants within sites will be handled with the SEM model in Mplus described above.

- **H3a** A significantly greater proportion of the FIT Teens group will achieve clinically meaningful reduction (i.e., a decrease in at least 7.8 points) in functional disability at 3-month follow-up than CBT.
- **H3b** A significantly greater proportion of the FIT Teens group will achieve clinically meaningful reduction (i.e., a decrease in at least 7.8 points) in functional disability at 3-month follow-up than GAE.

To test changes in the dichotomous (improved vs not improved) endpoints of functional disability from baseline to 3-month follow-up, baseline FDI scores will be subtracted from the 3-month follow-up FDI to identify those who did and did not achieve a clinically significant FDI change score. Results will be analyzed via separate difference between two independent proportions analyses for FIT vs. CBT & FIT vs. GAE testing  $H_0$ : 50% of participants in the three study arms will achieve a reliable FDI decrease versus  $H_A$ : 55% of participants in the FIT arm, and 35%-40% of participants in each of the CBT and GAE arms, will achieve a clinically significant FDI decrease.

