The design of this study is a multi-site RCT with 3 treatment arms (FIT, CBT and GAE). The main scientific focus of this trial is the efficacy of the treatments and maintenance of treatment effects over time. The treatments are designed to be group-based and patients will be randomized to receive treatment in small groups (clusters of 4-6 patients per group). We will recruit at multiple sites to ensure feasibility of achieving the necessary sample size. There will be equal numbers of patients in each of the treatment arms across sites (60 patients per site, 20 in each arm). Although site effects and effects of being assigned in particular "clusters" are not the primary focus of this study, we recognize the statistical issues that arise due to the nested nature of the design. The particular concern is of non-independence in outcomes among patients within the same group (cluster) and within the same sites regardless of treatment assignment. To handle the longitudinal design while also addressing potential bias that may influence results due to clustering, we considered 2 approaches for analyzing the continuous outcome of functional disability - multilevel modeling using a hierarchical linear model (HLM) approach and latent growth curve structural equation modeling (SEM). Both approaches can address the issue of clustering but an SEM approach was selected for several reasons -1) Longitudinal SEM & HLM have been shown to be equivalent analysis models, 2) a 'group * time' effect in HLM can be equated to 'slope on group' effect in SEM, and 3) although equivalent analysis models, research has shown SEM to have the greater statistical power.

E. Aim 1a

To test whether the combined FIT Teens intervention is more effective in reducing functional disability than CBT alone or GAE alone. **H1a.** The FIT Teens group will show significantly greater reduction in functional disability at 3-month follow-up compared to CBT and GAE, respectively.

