#### 5.0 Randomization

Participants will be randomized into FIT, CBT or GAE groups based upon a randomization schedule maintained by the study biostatistician. A randomization process *by group* will be used. In other words, after a sufficient number of approximately 4 to 6 patients have been screeened at a site and found to be eligible, the biostatistician will inform the therapist of the next group assignment. Randomization will be stratified by site in order to ensure approximately equal proportions of patients from each site in each of the 3 arms. Group assignments will be masked to the PI and study assessors. The study biostatistician ([name]) will monitor the equivalence of sample size in each treatment arm and at study mid-point will make any adjustments to the randomization schedule in consultation with the DSMB to ensure approximately equal group sizes by the end of the study.

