# 6.0 Derivations and Definitions

## Variable Definitions

# Demographics and Study Status

Variable	Descriptor	Derivation (if applicable)
Site	Institution Name	
SiteID (derived)	Site ID Number	IF Site=Cincinnati Children's Hospital Medical Center, 10; IF Site= Children's Mercy Hospitals and Clinics, 30; IF Site=Connecticut Children's Medical Center, 40; IF Site= Nationwide Children's Hospital, 50; IF Site= The Hospital for Sick Children, 60; IF Site= Boston Children's Hospital, 70; IF Site= Indianapolis Riley Children's Hospital, 80
Subject	Study ID [2-digit site ID]-[3-digit subject ID]	
mGROUP	Masked Group Assignment (A, B, C)	(From Randomization Record) (mGROUP to be edited to GROUP after primarily analysis complete)
GROUP	Group Assignment (CBT, FIT, GAE)	(From Randomization Record)
FORMAT	Treatment Delivery Format (In-person=1, Remote=2)	(From Randomization Record)
COHORTID_STD	Cohort ID (01-18)	
RFENROLLDTE_R AW	Date of Enrollment (Signed Consent)	
BRTHDAT_RAW	Participant's date of birth	
SEX_STD	Participant's sex 1=male; 2=female; 99 = other	
RACE_STD	Participant's race	Variable Labels: 1=More than one race; 2=Caucasian/White; 3=African American/Black; 4=Asian; 5=Native Hawaiian/Other Pacific Islander; 6= American Indian/Alaskan Native
ETHNIC_STD	Participant's ethnicity	Variable Labels: 1=Hispanic; 2=Non-Hispanic
INCOME_STD	Family Income	Variable Labels: 1=Less than \$24,999; 2=\$25,000 - \$49,999;

Beschipton	Derivation (il applicable)
•	3=\$50,000 - \$74,999;
	4=\$75,000 - \$99,999;
	5=\$100,000 - \$124,999;
	6=\$125,000 - \$149,999;
	7=More than \$150,000;
	8=Prefer not to answer;
	99=Unknown
Insurance Status	Variable Labels:
	1=Private Health Insurance;
	2=Medicare; 3=Medicaid;
	4=Military Health Care; 5=State
	Specific; 6= Indian Health
	Services; 7=Non-Us; 8=Other; 9
	= None
Caregiver 1	Variable Labels:
	1=Mother; 2=Father; 3=Legal
	Guardian
Caregiver 1 level of education	Variable Labels:
	1=Less than High School;
	2=High School/GED; 3=Partial
	College or Trade School;
	4=College Graduate; 5=Post
O and altern O	Graduate Degree
Caregiver 2	Variable Labels:
	1=Molner; 2=Faller;
Coregiver 2 level of education	3=Legal Guardian
Caregiver 2 level of education	1-Loss than High School:
	2-High School/CED: 2-Dartial
	College or Trade School:
	A=College Graduate: 5=Post
	Graduate Degree
Participant's grade enrolled	Variable Labels
r a topanto grado chiolica	$1=5^{\text{th}}$ $2=6^{\text{th}}$ $3=7^{\text{th}}$ $4=8^{\text{th}}$ $5=9^{\text{th}}$

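### The primary GEE clusters on the participant, not on the randomised treatment cohort, so any positive within-cohort correlation inflates the type I error of H1a and H1b

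*SAP*

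**What the plan says.** SAP 5.0 (Randomization) allocates by group. Once about 4 to 6 eligible patients are available at a site, "the biostatistician will inform the therapist of the next group assignment". SAP 3.0 gives cohort sizes of 3 to 6. Allocation is stratified by site.

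SAP 6.3 describes four nested levels: assessments, participants, cohorts and sites. It says that cohort and site variation has to be handled correctly to avoid biased effects and wrong inferences. It then chooses GEE, in which "every unique combination of participant (level 2), cohort (level 3), and site (level 4) will be used to indicate non-independent (i.e., correlated) responses". The H1a/H1b paragraph repeats this as "specifying every unique combination of participant (level 2), cohort (level 3), and site (level 4) as indicators of non-independent (correlated) responses" and places it in the Repeated specification.

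For H3a/H3b, SAP 6.3 says: "Results will be analyzed via separate difference between two independent proportions analyses for FIT vs. CBT & FIT vs. GAE".

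Protocol 5.D names non-independence among patients in the same treatment group as the particular concern of the nested design. Protocol 5.E (Aim 1a) plans a different primary analysis: a longitudinal SEM with site as the clustering variable and a saturated model at the patient-cluster level.

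**The concern.** In a GEE, two responses are treated as correlated only if they share the subject identifier, and the sandwich variance sums over those subjects as independent units. The unit should be no smaller than the unit of randomisation. Here the identifier is the combination of participant, cohort and site. Since participants are nested in cohorts and cohorts in sites, adding cohort and site to the identifier changes nothing. The subject ID already carries the site code.

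Patients in a cohort share therapists, sessions and peers. SAP 6.3 itself expects social support, better engagement and less dropout from the group format. If these make cohort-mates' changes in FDI alike, that shared variation goes straight into the comparison of arms and the planned standard errors leave it out. The confidence intervals for both primary contrasts would be too narrow, and a superiority claim could rest on an error rate well above 5%.

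**Working it through.** **Inputs from the documents**
- Cohort size m: 3 to 6 (SAP 3.0), 4 to 6 (SAP 6.3).
- Analysed sample: 105 per arm, N = 315 (SAP 4.0).
- Effects: FIT 0.90, CBT 0.52, GAE 0.40 in SD units (SAP 4.0). The differences are 0.38 (FIT vs CBT) and 0.50 (FIT vs GAE).
- Two-sided alpha 0.05 (SAP 6.0, Statistical Analyses).

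**Assumed:** an ICC for FDI change within cohorts of 0.01 to 0.15, because the documents give none.

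**Step 1. What the identifier does.** A mock data set had 315 participants in 63 cohorts of 5 at 7 sites. Participant by cohort by site gave 315 clusters, not 63. GEE standard errors for the two group-by-time terms were identical to clustering on participant (0.0435 and 0.0462 both ways). One data set shows this identity; it does not show the size of the inflation.

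**Step 2. The plan's own power figure.** Power = Φ(δ/√(2/n) − 1.96).
- FIT vs CBT: 0.38/√(2/105) = 2.753, so power = Φ(0.793) = 0.786. The SAP states 0.79.
- FIT vs GAE: power = 0.952. The SAP states above 0.80.

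The stated 0.79 therefore matches a calculation for independent patients. This is a closed-form match, not a rerun of the Mplus simulation.

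**Step 3. True error if cohorts are ignored.** Design effect DE = 1 + (m − 1) × ICC. True alpha = 2 × [1 − Φ(1.96/√DE)].

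| ICC | m = 3 | m = 4 | m = 5 | m = 6 |
|---|---|---|---|---|
| 0.01 | 5.2% | 5.4% | 5.5% | 5.6% |
| 0.02 | 5.5% | 5.7% | 5.9% | 6.2% |
| 0.05 | 6.2% | 6.8% | 7.4% | 8.0% |
| 0.10 | 7.4% | 8.6% | 9.8% | 11.0% |
| 0.15 | 8.6% | 10.4% | 12.1% | 13.8% |

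For m = 5 the planned intervals are too narrow by 1 − 1/√1.20 = 9% at ICC 0.05 and 1 − 1/√1.40 = 15% at ICC 0.10.

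**Step 4. Simulation check.** Null true, 21 cohorts of 5 per arm, 20,000 trials per ICC, change score at 3 months. Participant-level robust errors rejected 5.2% at ICC 0, then 5.4%, 6.0%, 7.6%, 9.7% and 12.4% at ICC 0.01, 0.02, 0.05, 0.10 and 0.15. Cohort-level errors with a t reference rejected 4.8% to 4.9% throughout.

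**Step 5. Power with the cohort as unit (m = 5, n replaced by 105/DE).**

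| ICC | DE | FIT vs CBT | FIT vs GAE | n per arm for 80%, FIT vs CBT |
|---|---|---|---|---|
| 0.01 | 1.04 | 0.77 | 0.94 | 114 |
| 0.05 | 1.20 | 0.71 | 0.91 | 131 |
| 0.10 | 1.40 | 0.64 | 0.87 | 153 |

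**The case against.** The literal reading is hard to dispute; the objections concern size and context.

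- **The harm depends on the ICC.** This stands. At ICC 0.01 the inflation is slight (5.2% to 5.6%). H1 tests a difference in slopes, so stable differences in FDI level between cohorts largely cancel, and the delivery-format term may absorb some of the rest. But a confirmatory test should not depend on an unstated assumption that the ICC is zero when the plan itself expects cohort effects.
- **Cohorts may be smaller than 5.** With 20% attrition a cohort of 5 averages 4 observed members, and the m = 4 column applies: 6.8% at ICC 0.05.
- **Site stratification offsets part of it.** This is true if site is left out of the model. With balanced cohorts of 5, true over assumed variance is (5σ²c + σ²e)/(σ²s + σ²c + σ²e), where s, c and e denote site, cohort and residual. Cohort variance 0.05 with site variance 0.05 gives (0.25 + 0.90)/1 = 1.15, or 6.8%. Site variance 0.10 gives (0.25 + 0.85)/1 = 1.10, or 6.2%. Simulations with site variance omitted from the model gave 6.3% to 7.3%. The inflation vanishes only if site variance reaches four times cohort variance.
- **The documents contain a cohort-aware method.** Protocol 5.E has one for H1a, and SAP 6.4 keeps it for pain at 3 months. Neither governs the SAP's H1 analysis, which is the GEE. The three-level model in SAP 6.5.1 is for imputation and does not change the GEE's standard errors.
- **H3 is not a GEE.** Correct: no identifier is mis-specified there. The consequence is the same, because a test of independent proportions also ignores the randomised cohort.

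**Conclusion.** Wrong as written. The SAP's identifier reduces to the participant, so the primary analysis leaves out the randomised unit that both documents say must be accounted for. Nothing elsewhere in the SAP repairs the H1 standard errors or the H3 test. For cohorts of 3 to 6 and an assumed ICC of 0.05 to 0.10, the real two-sided error per primary contrast is about 6.2% to 11.0%, with some offset if site differences are large and left out of the model. The direction rests only on a positive within-cohort correlation; the size rests on an ICC that the documents do not give. This must be fixed because it affects both primary contrasts.

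**What to change.** In SAP 6.3, define the GEE cluster as site by cohort, with each participant's repeated measures nested inside it. COHORTID_STD runs only from 01 to 18, so cross it with the site ID. N = 315 gives about 53 to 79 cohorts at sizes 6 to 4, and up to 105 at size 3. Specify a small-sample-corrected sandwich variance and t degrees of freedom based on the number of cohorts, with site as a fixed stratification factor. Replace the H3 test with a binomial GEE clustered the same way. A mixed model with a cohort random effect, or the cohort-level SEM of Protocol 5.E, would also serve. In either case, reconcile the SAP with Protocol 5.E. Also settle the H2 paragraph, which relies on an SEM described above in the SAP although section 6.3 describes none.

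State an assumed ICC and redo the power statement in SAP 4.0. All of this should be settled before group labels are unmasked.

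The cost is SAP text and minor programming, since cohort ID is already collected. For cohorts of 5, intervals become about 10% wider at ICC 0.05 (√1.20 = 1.095) and 18% wider at ICC 0.10 (√1.40 = 1.183). Power for FIT vs CBT is then about 0.71 or 0.64 against the stated 0.79. The planned GEE hides this loss; the correction does not cause it.

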#### Aim 1c. Proportion of patients achieving clinically meaningful change.

We anticipate that the FIT Teens intervention will result in a greater proportion of patients achieving the binary outcome of clinically meaningful reduction in FDI compared to CBT and GAE. This difference is expected to be between 15%-20% based on our pilot study of FIT teens and our previous trial of CBT showing ~55% of the FIT group and 35-40% of CBT participants achieving clinically meaningful change. The proportion of GAE patients achieving this binary outcome is expected to be similar to CBT. Power was calculated via G\*Power3 assuming proper handling of missing data and n = 105 within the three arms available for analysis. Results showed power will be 0.79 for either the FIT vs. CBT or FIT vs. GAE comparison if difference between two independent proportions is at least 17% or greater (False Discovery Rate Type-1 error control will be used to evaluate results from both tests). A difference in proportion of  $\geq 17\%$  between FIT Teens and CBT or GAE will provide useful information for patients and providers about the relative efficacy of the interventions in achieving clinically meaningful improvement in functioning.

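### The responder aim (H3) has a misworded null, and its plain two-proportion test conflicts with SAP 6.3's own requirements on GEE, delivery format, site and cohort

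*SAP*

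**What the plan says.** SAP 2.0 lists the responder comparison as a primary aim (Aim 3). H3a and H3b say that a larger share of FIT patients than of CBT or GAE patients will have an FDI fall of at least 7.8 points at 3 months. For the analysis, SAP 6.3 names "separate difference between two independent proportions analyses for FIT vs. CBT & FIT vs. GAE" and states the null as "50% of participants in the three study arms will achieve a reliable FDI decrease", against an alternative of 55% in FIT and 35-40% in each comparator. Protocol 5.G has the same text. No covariate, stratum or cluster term is attached.

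The opening of SAP 6.3 sets general rules:
- Primary and secondary aims are to be analysed by GEE.
- Cohort and site variation must be handled before treatment effects are tested.
- The format indicator "will be included as a moderator in all analyses to model the effect of delivery format", and the need for format-by-group terms is to be tested.

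SAP 5.0 randomises by group, once about 4 to 6 eligible patients are available, and says: "Randomization will be stratified by site".

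The planning rates are in SAP 4.0, Aim 1c: "55% of the FIT group and 35-40% of CBT participants achieving clinically meaningful change", and for GAE "The proportion of GAE patients achieving this binary outcome is expected to be similar to CBT". Baseline FDI enters H3 only through the change score. Under SAP 6.2 it is otherwise a candidate covariate if the arms differ at baseline with p < .10.

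**The concern.** There are two separate problems, of unequal weight.

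The first is the null. A claim that FIT beats a comparator needs a null of equal proportions at whatever common rate holds. Fixing that rate at 50% adds a condition that H3 does not contain. It also disagrees with the plan's own figures: 55% with 35% averages (55 + 35)/2 = 45%, and 55% with 40% averages 47.5%.

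The second is the test. A bare comparison of two proportions treats patients as independent and uses no other variable. It therefore cannot follow the rules at the start of the same section. Patients are allocated and treated in cohorts, so outcomes within a cohort may be correlated, as Protocol 5.D acknowledges. Ignoring positive correlation makes the p-values of a primary-aim comparison too small and its intervals too narrow. An analyst cannot follow both parts of SAP 6.3 for H3.

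**Working it through.** **Inputs from the documents.** 105 per arm ("n = 105 within the three arms available for analysis"); a 17-point difference ("if difference between two independent proportions is at least 17% or greater"), taken here as 55% versus 38%; two-sided alpha 0.05 (SAP 6.0); cohorts of 4 to 6 (SAP 6.3). The documents give no ICC, so 0.01 to 0.10 is an assumption.

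**1. The plan's power figure.** Let p̄ = (0.55 + 0.38)/2 = 0.465.
- Null SE = √(2 × 0.465 × 0.535/105) = 0.0688.
- Alternative SE = √((0.55 × 0.45 + 0.38 × 0.62)/105) = 0.0678.
- Two-sided power = Φ((0.17 − 1.96 × 0.0688)/0.0678) = 0.697.
- With 1.645 (one-sided 5%) it is 0.799.

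The SAP's 0.79 is therefore not reproduced at two-sided 0.05 and is approached only one-sided. That is a separate matter. What counts here is whether the 50% explains it. With the null SE at 50%, √(2 × 0.25/105) = 0.0690, two-sided power is 0.696. The 50% makes almost no difference.

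**2. Does the 50% null distort the named test?** Exact enumeration of the pooled two-sample z test, 105 independent patients per arm, two-sided 0.05:

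| Common response rate | Type I error |
|---|---|
| 35% | 0.051 |
| 40% | 0.051 |
| 50% | 0.045 |

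Under independence the named test is valid for equality at each of these rates.

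**3. Ignoring the cohort.** Design effect DE = 1 + (m − 1) × ICC for cohort size m. The true error of an independence test run at 5% is 2 × (1 − Φ(1.96/√DE)). Cluster-adjusted power uses 105/DE per arm.

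| m | ICC (assumed) | DE | True type I error | Adjusted power, 55% vs 38% |
|---|---|---|---|---|
| 4 | 0.01 | 1.03 | 0.053 | 0.685 |
| 4 | 0.10 | 1.30 | 0.086 | 0.583 |
| 5 | 0.05 | 1.20 | 0.074 | 0.617 |
| 6 | 0.01 | 1.05 | 0.056 | 0.676 |
| 6 | 0.10 | 1.50 | 0.110 | 0.523 |

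**4. Can the H1 cluster definition be reused?** SAP 6.3 defines correlated responses for GEE by each unique combination of participant, cohort and site. With repeated FDI scores, that groups a patient's own visits. H3 has one binary response per patient, so every such cluster has size m = 1 and DE = 1 + 0 × ICC = 1. Members of the same cohort would still be treated as independent.

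**5. Baseline FDI.** Simulations at 55% versus 40%, 105 per arm, compared response models with and without baseline FDI. The inputs are assumptions: baseline N(22, 9) truncated at 13 (the entry threshold in Protocol 3.C), change SD 10.3, and slopes of change on baseline of 0.3, 0.5 and 0.7. Across separate runs power rose by about 2-3, 5-6 and 8-11 points respectively. For scale, unadjusted two-sided power at 55% versus 40% is 0.587. The simulations contained no cohort effect and say nothing about step 3.

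**The case against.** The strongest reply on the null is that the named method compares the arms with each other, and 50% in every arm is just one instance of equality. Step 2 bears this out. A reader might infer that the plan would declare a FIT benefit when all arms respond equally at, say, 40%. A literal joint test that two arms are each at 50% would indeed reject 0.746 of the time in that case. But no section plans such a test or a pooled comparison against 50%, so that inference is not supported.

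On the test, the general GEE rule in SAP 6.3 can be read as already covering H3, which is a primary aim, and a binary GEE can carry format and site. That is fair: the documents contradict themselves rather than clearly choosing an unadjusted analysis. The conflict stands, because the H3 text is the specific instruction and has none of these terms.

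A reader might also treat the absence of baseline FDI as an error. No section requires it for H3, and entry at FDI of 13 or more leaves room for a 7.8-point fall in every patient. Adjustment is a matter of efficiency only.

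**Conclusion.** The concern holds in a limited form. The H3 null is misworded in both documents; it should be corrected, but it changes almost nothing if the named test is run. The conflict over method matters more: as written, the H3 test leaves out delivery format, site and cohort, contrary to the same SAP section. Its size depends on an ICC that the documents do not supply. Over 0.01 to 0.10 the true type I error is about 5.3% to 11%: negligible at the low end and about double the nominal level at the high end. These are design-effect approximations with equal cohort sizes and the stated 105 analysed per arm. The baseline FDI gain of about 2 to 11 power points is conditional on the assumed inputs and corrects no error. This should be settled before the analysis.

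**What to change.** In SAP 6.3 and Protocol 5.G:
- State H0: pFIT = pCBT and H0: pFIT = pGAE, two-sided. Delete the 50% null and keep the 55% and 35-40% figures in the power section only.
- Replace the two-proportion test with a logistic GEE or mixed model for response, with arm, site, delivery format and baseline FDI as a prespecified precision covariate. Test the format-by-arm terms as SAP 6.3 already provides.
- Define clusters for H3 at cohort level, not as the participant-cohort-site combination used for H1.
- Report standardised risk differences with 95% CIs beside the raw responder proportions. Keep the False Discovery Rate control that SAP 4.0 names for the two tests.

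The cost is a few lines of text and code in each document; baseline FDI, site, format and cohort are already collected. The downsides are that the estimate is model-standardised, which the raw proportions offset, and that intervals will be wider where cohort correlation is present. That width is correct: at DE = 1.50 the standard error grows by √1.50 = 1.22.
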